7.4.2 Analysis of Co-Primary Endpoint of CR/CRh Rate (First Interim only)

The co-primary efficacy endpoint of CR/CRh rate will be evaluated at the first interim analysis only. The two-sided 95% exact confidence interval of CR/CRh rate will be calculated for approximately 141 subjects who are randomized into ASP2215 arm and at least 112 days (4 treatment cycles) post first dose or randomization (for subjects who received no study drug), i.e., 2215 subjects in RAS. The lower limit will be used to compare with the benchmark of CR/CRh rate of 12%.

CR/CRh rate along with the two-sided 95% exact confidence interval based on binomial distribution will be calculated using SAS code similar to that shown below:

The sensitivity analysis for CR/CRh rate will be performed to assess the robustness of the CR/CRh rate as follows:

- The same analysis as primary analysis but only including subjects in mRAS
- The same analysis as primary analysis but only including subjects who took at least one dose of ASP2215
- The same analysis as primary analysis but only including subjects who had at least one post baseline bone marrow assessment
- Apply the same analysis method used for primary analysis to evaluate CR/CRh rate by cycle 4 (as defined in Section 6.1.2)

• Apply the same analysis method used for primary analysis to evaluate CR/CRh rate prior to HSCT (as defined in Section 6.1.2)

7.4.3 Analysis of Secondary Endpoints

7.4.3.1 Key Secondary Efficacy Analysis

The key secondary efficacy endpoint of EFS will be analyzed in the same manner as the co-primary endpoint of OS. In order to compare the EFS between ASP2215 and the salvage chemotherapy, the null hypothesis will be constructed:

• H₀₂: EFS in ASP2215 is worse or equal to EFS in salvage chemotherapy

The accompanying alternative hypothesis is:

• H₁₂: EFS in ASP2215 is better than EFS in salvage chemotherapy

To maintain the overall 1-sided Type I error rate at the 0.0245 significance level, the key secondary efficacy endpoint of EFS will be tested only at second interim and final analyses and only if the null hypothesis on OS (H_{01}) is rejected. The test significance levels of EFS endpoint at the second interim and final analyses are specified in Table 4.

The one-sided p-value for the above hypothesis test will be performed using the stratified log-rank test with strata (per IRT) to control for response to first-line AML therapy and preselected salvage chemotherapy.

The hazard ratio of the treatment effect along with 95% confidence interval will be calculated using stratified Cox proportional hazard model. The same stratification factors will be applied to both the stratified log-rank test and the stratified Cox proportional hazard model. The same Cox proportional hazard model will be included as a sensitivity analysis for testing H_{03} .

Kaplan-Meier survival plots will be used to describe the EFS in each treatment group. Median EFS and 95% confidence interval, EFS rates at 6, 12, 24 and 36 months and 95% confidence interval will be estimated from the Kaplan-Meier curve. The number and percentage of EFS event (relapse, death or treatment failure) and censoring will be summarized for each treatment group.

The sensitivity analyses for the key secondary efficacy endpoints of EFS include:

- The same analysis as primary analysis but on FAS
- The same analysis as primary analysis but on PPS
- Stratified Cox proportional hazard model with strata to control for response to firstline AML therapy and preselected salvage chemotherapy on ITT
- The same analysis as primary analysis but with the date of the first new anti-leukemia therapy after the end of study treatment or the last treatment evaluation date (when the date of new anti-leukemia is not available) will be used as the event date of treatment failure as defined in Section 6.1.3.1
- The same analysis as primary analysis but with "Lost to follow up" also considered as an EFS event as defined in Section 6.1.3.1. "Lost to follow up" event includes

subjects who discontinued either study treatment or study follow up (including 30 day and long term follow up) due to either "LOST TO FOLLOW-UP" or "WITHDRAWAL BY SUBJECT". For subjects who discontinued the study treatment due to "WITHDRAWAL BY SUBJECT", only those who revoked the authorization to follow up will be included.

- The same analysis as primary but consider the subjects who discontinued the treatment and only achieved best response of NR as treatment failure as defined in Section 6.1.3.1.
- The same analysis as primary but consider the subjects who discontinued the treatment with post-treatment disease assessment and achieved best response of PR, NR or NE as treatment failure as defined in Section 6.1.3.1.
- The same analysis as primary but consider using long term follow up data of Death and new AML therapies. The new AML therapies captured on CRF page will only be considered as event when the patient did not relapse per derived response.

The key secondary efficacy endpoint of CR rate will be analyzed using the Cochran-Mantel-Haenszel (CMH) test to control for response to first-line AML therapy and preselected salvage chemotherapy (Per IRT) on ITT. In order to compare the CR rate between ASP2215 and the salvage chemotherapy, the null hypothesis will be constructed:

• H₀₃: CR rate in ASP2215 arm is lower than or equal to the CR rate in salvage chemotherapy arm

The accompanying alternative hypothesis is:

• H₁₃: CR rate in ASP2215 arm is higher than in salvage chemotherapy

To maintain the overall 1-sided Type I error rate at the 0.0245 significance level, the key secondary efficacy endpoint of CR rate will be tested only at second interim and final analyses and only if the null hypothesis on OS (H_{01}) and EFS (H_{02}) are rejected hierarchically. The test significance levels of CR rate endpoint at the second interim and final analyses are specified in Table 4.

The treatment difference along with 95% confidence interval will be calculated using Mantel-Haenszel estimate.

The SAS code to implement the above test will be similar to that shown below:

```
PROC FREQ;
     TABLES stratification variables * response * treatment/cmh;
RUN;
```

CR rate along with the two-sided 95% exact confidence interval based on binomial distribution will be calculated for each treatment group using SAS code similar to that shown below:

```
PROC FREQ;
```

```
TABLES outcome/BIONOMIAL (EXACT);
BY treatment;
RUN:
```

The sensitivity analysis for CR rate will be performed as following:

- The same analysis as primary analysis but on FAS
- The same analysis as primary analysis but on PPS
- The same analysis as primary analysis but only including subjects who received at least one dose of study treatment
- The same analysis as primary analysis but only including subjects who had at least one post baseline bone marrow assessment
- Apply the same analysis method used for primary analysis to evaluate CR rate prior to HSCT (as defined in Section 6.1.3.1)
- Un-stratified Fisher's exact test on ITT
- The same analysis as primary analysis for CR rate will be performed by dose adjustment in ASP2215 arm.

7.4.3.2 Other Secondary Efficacy Analysis

At the first interim analysis, Duration of CR/CRh (DCRCRh) will be summarized descriptively by median, corresponding 95% confidence interval and range as estimated from the Kaplan-Meier curve. DCRCRh will be analyzed for subjects who achieved either CR or CRh in the same analysis set of CR/CRh rate. Duration of CRh (DCRh) will also be summarized similarly as duration of CR/CRh but for subjects who achieved CRh only.

Transfusion status (independent vs. dependent) at baseline period and post-baseline period will be summarized in a two-by-two contingency table.

Transfusion conversion rate and transfusion maintenance rate will be calculated based on the transfusion status. 95% confidence interval will be presented for both transfusion conversion and maintenance rates.

LFS and duration of remission (including DCRc, DCR, and DR) will be analyzed for subjects who achieved remission using the stratified log-rank test with strata to control for response to first-line AML therapy and preselected salvage chemotherapy. The hazard ratio of the treatment effect along with 95% confidence interval will be calculated. The survival curve and the median will be estimated using the Kaplan-Meier method and will be reported along with the corresponding 95% confidence interval.

CRc rate and transplantation rate will be analyzed in the same manner as CR rate using CMH test to control for response to first-line AML therapy and preselected salvage chemotherapy. The number and percentage of subject with CRc and transplantations will be summarized for each treatment group along with exact 95% confidence interval based on binomial distribution. The treatment difference along with 95% confidence interval will also be calculated. The CRc rate will be summarized by dose adjustment in ASP2215 Arm.

BFI global fatigue score will be summarized using mean, standard deviation, minimum, maximum and median by treatment group at each visit. Additionally, a within-subject change will be calculated as the post-baseline measurement minus the baseline measurement and summarized in the same way. Change from baseline BFI score will be analyzed using Analysis of Covariance (ANCOVA) including treatment as a fixed factor, baseline BFI score, response to first-line AML therapy and preselected salvage chemotherapy as covariates.

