- k. For MEC and FLAG-IDA, bone marrow samples are required during screening and cycle 2 day 1. Also, an additional bone marrow sample is required at cycle 1 day 15 or later, per institutional guidelines, to assess the need for a second cycle. For LoDAC or azacitidine, bone marrow samples are required during screening, and at cycle 2 day 1 and at cycle 3 day 1. For subjects who do not achieve a CRc (CR, CRp or CRi), the bone marrow assessments will be repeated at day 1 of every 2 subsequent cycles. For subjects who achieve a CRc (CR, CRp or CRi), bone marrow sampling will be repeated at 1 month after the date of remission and every 3 subsequent cycles, or if there is suspicion of relapse in the whole blood. Bone marrow samples are also required at the end of treatment visit and as clinically indicated. If bone marrow aspirate is unobtainable (e.g., dry tap), an additional EDTA tube of peripheral blood should be collected instead. Bone marrow aspirate is required, and bone marrow biopsy is preferred. In case of inadequate aspirate, bone marrow biopsy is required.
- 1. Whole blood and buccal swab collected at day 1 for optional pharmacogenomic study.
- m. LoDAC or azacitidine dosing may continue past cycle 2.
- n. Additional clinic visits are allowed per institutional guideline for subjects receiving MEC (days 1 through 5) or FLAG-IDA (days 1 through 6). MEC and FLAG-IDA are administered for up to 2 cycles depending on response and safety assessments as described in Section 5.1 of the protocol.
- o. Chest X-ray (or CT of chest) does not need to be repeated if performed within 2 weeks prior to start of screening.
- p. For the purposes of drug preparation and dispensing activities, IRT transaction may be done prior to the visit and do not need to fall within the protocol visit window.

Footnotes continued on next page.

- q. Includes Brief Fatigue Inventory, Functional Assessment of Chronic Illness Therapy–Dyspnea-Short Forms, Functional Assessment of Cancer Therapy-Leukemia and dizziness and mouth sores items. The BFI will be administered at cycle 1 day 1 predose, cycle 1 day 8 (± 1 day), day 15 (± 1 day), cycle 2 day 1 (± 2 days), day 15 (± 1 day) and all subsequent cycles day 1 (± 2 days). Functional Assessment of Chronic Illness Therapy–Dyspnea-Short Forms, Functional Assessment of Cancer Therapy-Leukemia and dizziness and mouth sores items will be administered at cycle 1 day 1 predose, cycle 2 day 1 (± 2 days) and all subsequent cycles day 1 (± 2 days).

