- e. For subjects who plan to proceed to HSCT and resume ASP2215 treatment after HSCT, AE collection will continue until the start of the HSCT conditioning regimen and AE collection will resume upon the resumption of ASP2215 treatment until 30 days after the last dose of study drug. For subjects who do not plan to resume ASP2215 treatment after HSCT, AE collection will continue until the start of the HSCT conditioning regimen or 30 days after the last dose of study drug, whichever comes first. However, the following AE/SAEs will continue to be collected until 30 days after the last dose of study drug, regardless of the time of the HSCT conditioning regimen:
 - Any study drug related AE that is ongoing will be followed until resolved
 - Any SAE that is deemed to be related to study drug by the investigator
 - Any event of veno-occlusive disease (VOD) of the liver, cardiac failure, Grade 3 or higher QT prolongation, rhabdomyolysis, drug-induced liver injury, or PRES
 - Adverse events leading to death
- f. Telephone contact with the subject is sufficient unless any assessment must be repeated for resolution of treatment-related AEs.
- g. Only SAE data that is related to ASP2215 will be collected.
- h. Telephone contact every 3 months. Ad hoc contact will be required during interim analysis.
- i. Includes Brief Fatigue Inventory, Functional Assessment of Chronic Illness Therapy—Dyspnea-Short Forms, Functional Assessment of Cancer Therapy—Leukemia and dizziness and mouth sores items. The BFI will be administered at pre-HSCT/end of treatment visit. Functional Assessment of Cancer Therapy—Dyspnea-Short Forms, Functional Assessment of Cancer Therapy—Leukemia and dizziness and mouth sores items will be administered at pre-HSCT/end of treatment visit.
- j. Ophthalmologic assessment to be performed by visual acuity measurement and ophthalmoscopy, at the Pre-HSCT/end of treatment (+/- 7 days). In symptomatic subjects, the ophthalmologic assessment should also include slit lamp biomicroscopy, visual fields and optical coherence tomography (OCT).
- k. If possible, patient reported outcome measures should be performed prior to any other assessments on that visit day.

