3.2 Study Design

3.2.1 Study Design

This is a phase 3, open-label, multicenter, randomized study to compare the efficacy and safety of ASP2215 therapy to salvage chemotherapy in FLT3-mutated AML subjects who are refractory to or have relapsed after first-line AML therapy. Approximately 140 centers in North America, Europe, Asia and rest of the world will participate in this study.

Three hundred sixty nine subjects will be randomized. The randomization of the 369 subjects will be in a 2:1 ratio to receive ASP2215 or salvage chemotherapy. Subjects will enter the screening period up to 14 days prior to the start of treatment. Prior to randomization, the Investigator will preselect a salvage chemotherapy regimen for each subject; options will include LoDAC, azacitidine, MEC or FLAG-IDA. The randomization will be stratified by response to first-line therapy and preselected salvage chemotherapy. Subjects will be administered treatment over continuous 28-day cycles and per institutional guidelines for chemotherapy product preparation and administration. The dose and duration of study treatments are outlined in Section 5.1.1 of the protocol.

For subjects taking ASP2215, LoDAC or azacitidine, treatment should continue until the subject meets a treatment discontinuation criterion.

Subjects receiving MEC or FLAG-IDA will receive 1 cycle of therapy and will be assessed for response on or after day 15, per institutional guidelines. If the bone marrow cellularity is

20% or greater with at least a 50% reduction in blasts, the subject may receive a second cycle of the same chemotherapy. If bone marrow cellularity is between 5% and 20%, the investigator should make the decision whether the subject should receive another treatment cycle or be observed for recovery. If bone marrow cellularity is 5% or less, the subject will be observed for recovery. Subjects achieving CR, CRi or CRp may receive a second cycle of chemotherapy at the Investigator's discretion. Subjects with no response (NR) or progressive disease following cycle 1 will discontinue study treatment.

Dose adjustments for ASP2215 are described in Section 5.1.2 of the protocol.

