Subjects who have a donor identified and achieve a response allowing them to undergo HSCT per each institution's assessment can undergo HSCT without leaving the study. However, ASP2215 should be stopped and a pre-HSCT visit should be performed prior to starting the conditioning regimen for HSCT. ASP2215 can be resumed after stem cell transplantation if the following conditions are met:

- Subject is between 30 60 days post HSCT
- Subject has had successful engraftment as demonstrated by absolute neutrophil count $(ANC) \ge 500/mm3$ and platelets $\ge 20000/mm3$ without transfusions
- Subject does not have \geq grade 2 acute graft-versus-host-disease (GVHD)
- Subject is in CRc

For subjects resuming treatment, subjects will follow the procedures listed under subsequent cycles day 1 in the Schedule of Assessments. Subjects who do not resume ASP2215 will be followed for OS endpoint.

After treatment discontinuation, subjects will have a pre-HSCT/end of treatment visit within 7 days after treatment discontinuation, followed by a 30-day follow-up visit in which a telephone contact with the subject is sufficient unless any assessment must be repeated for resolution of treatment-related AEs. After which the subjects will enter the long-term follow-up period for collection of patient reported outcome (PRO) using EQ-5D-5L, subsequent AML treatment, remission status and survival (cause of death and date of death). The long-term follow-up will be every 3 months, for up to 3 years from the subject's end of treatment visit.

Two interim analyses by an Independent Data Monitoring Committee (IDMC) will be conducted. The first interim analysis is planned when approximately 141 subjects are randomized into ASP2215 arm and at least 112 days (4 treatment cycles) post first dose or randomization (for subjects who received no study drug). The first interim analysis will be performed to evaluate the efficacy endpoint of CR/CRh rate and the study conduct will not be impacted by the result of the CR/CRh rate.

The second interim analysis will be performed when approximately 50% of the planned total number of deaths (death events =129 of planned 258 death events) by any cause have occurred. The second interim analysis will be utilized to determine whether the study should be terminated earlier than planned if ASP2215 has more favorable or harmful outcome than

the salvage chemotherapy group. Details of the interim analyses are described in Section 7.10.

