6.1.3.2 Other Secondary Efficacy Endpoints

• Leukemia-free survival (LFS)

LFS is defined as the time from the date of first CRc until the date of documented relapse (excluding relapse from PR) or death for subjects who achieve CRc (relapse date or death date – first CRc disease assessment date + 1). For a subject who is not known to have relapsed or died, LFS is censored on the date of last relapse-free disease assessment date (last relapse-free disease assessment date – first CRc disease assessment date + 1).

- Complete Remission with Partial Hematologic Recovery (CRh) Rate
 CRh rate is defined as the number of subjects who achieve CRh at any of the post
 - baseline visits and do not have best response of CR divided by the number of subjects in the analysis population.
- Composite Complete Remission (CRc) Rate

CRc rate is defined as the number of subjects who achieve the best response of CRc (CR, CRp or CRi) divided by the number of subjects in the analysis population.

• Duration of remission

Duration of remission includes duration of CRc (DCRc), duration of CR/CRh (DCRCRh), duration of CRh (DCRh), duration of CR (DCR), and duration of response (DR) (i.e., CRc + PR).

Duration of CRc is defined as the time from the date of first CRc until the date of first documented relapse for subjects who achieve CRc (relapse date – first CRc disease assessment date + 1). Subjects who die without report of relapse are considered non-events and censored at their last relapse-free disease assessment date (last relapse-free disease assessment date – first CRc disease assessment date + 1). Other subjects who do not relapse on study are considered non-events and censored at the last relapse-free disease assessment date.

Duration of CR/CRh is defined similarly as duration of CRc for subjects who achieve either CR or CRh. For subjects who achieve both CR and CRh, the first date will be used as the starting date of the duration.

As a sensitivity analysis, Duration of CR/CRh will be defined similarly as the above, however deaths without report of relapse are considered as events.

Duration of CRh is defined similarly as duration of CRc for subjects who achieve CRh.

Duration of CR is defined similarly as duration of CRc for subjects who achieve CR.

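### Scheduled relapse assessment for MEC/FLAG-IDA remitters is not clearly fixed beyond treatment, so the tests of LFS and duration of remission cannot separate durability from assessment schedule

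*SAP*

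**What the plan says.** **Treatment length.** For the intensive regimens, Table 2 footnote n says "MEC and FLAG-IDA are administered for up to 2 cycles depending on response and safety assessments". For the others, section 3.2.1 says "For subjects taking ASP2215, LoDAC or azacitidine, treatment should continue until the subject meets a treatment discontinuation criterion".

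**Marrow schedule.** Table 2 footnote k says "For MEC and FLAG-IDA, bone marrow samples are required during screening and cycle 2 day 1", with a further sample at cycle 1 day 15 or later. For chemotherapy subjects in CRc, without limit by regimen, it adds that "bone marrow sampling will be repeated at 1 month after the date of remission and every 3 subsequent cycles", or on suspicion of relapse. It also requires an end-of-treatment marrow. Table 1 footnote k gives ASP2215 subjects essentially the same rule.

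**After treatment.** Table 3 marks no marrow or laboratory test in the 30-day or long-term columns. Footnote h sets "Telephone contact every 3 months". Section 3.2.1 lists remission status and subsequent AML treatment among the items collected in that period.

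**Relapse and censoring.** Relapse rests on blasts or extramedullary disease (6.1.3.3). A disease assessment date comes from marrow, peripheral blood or extramedullary assessment (6.1.3.1). LFS counts relapse or death, with no time limit on death, and otherwise censors at the last relapse-free assessment (6.1.3.2). For duration of CRc, "Subjects who die without report of relapse are considered non-events and censored at their last relapse-free disease assessment date".

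**Analysis.** "LFS and duration of remission (including DCRc, DCR, and DR) will be analyzed for subjects who achieved remission using the stratified log-rank test" (7.4.3.2), with a hazard ratio. Section 7.4.6 carries the duration-of-CR method over to duration of CR/CRh. Long-term follow-up deaths and new AML therapies are used in one EFS sensitivity analysis (7.4.3.1). No such analysis is planned for LFS or duration of remission.

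**The concern.** A relapse endpoint compares arms fairly only if both arms are examined on a similar calendar. Here the calendar runs on treatment cycles, and cycles stop early for one part of the control arm. Stratifying by preselected chemotherapy does not help: within the high-intensity stratum, ASP2215 subjects go on cycling while their comparators do not. At stake is whether a reported difference in LFS or duration of remission reflects how long remissions last or how often someone looked.

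**Working it through.** The SAP gives no event count or power for these endpoints, so there is no planned figure to reproduce. The check sets the rules side by side and then works through their consequences.

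**1. Schedules for a subject in CRc**

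| | ASP2215 | LoDAC/azacitidine | MEC/FLAG-IDA |
|---|---|---|---|
| Treatment | until a discontinuation criterion | same | at most 2 × 28 = 56 days |
| Marrow after CRc | 1 month, then every 3 × 28 = 84 days | same | same words, but not said to run on after the last cycle |
| After end of treatment | telephone | telephone | telephone |

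**2. Two hypothetical remitters, days counted from remission.** Subject A relapses on day 150 and dies on day 270. Subject B stays in remission and is alive at day 540.

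- *On continuing ASP2215.* Marrows fall on days 30, 114, 198 and so on. A has an LFS and a duration event on day 198. B is censored on day 30 + 6 × 84 = 534.
- *On MEC/FLAG-IDA, last marrow day 30, no later sample.* A has an LFS event on day 270 and is censored for duration on day 30. B is censored for both on day 30.
- *On MEC/FLAG-IDA, with A sampled on suspicion of relapse on day 150.* A has both events on day 150. B is still censored on day 30.

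For LFS, A's late event date lowers the control hazard. Dropping B early while A stays at risk raises it. The two effects oppose each other, so the rules do not fix the sign. For duration, early censoring alone loses events. Bias appears once relapsers are sampled and non-relapsers are not.

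**3. Relapses after the last scheduled marrow.** Assume exponential relapse with median m months and a last marrow 1 month after remission. The share falling later is 2^(−1/m): 0.84 for m = 4, 0.89 for m = 6, 0.93 for m = 9. Counting only relapses within follow-up, simulation gives 0.82 to 0.90. This is the share exposed to being missed, not the share missed.

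**4. Numbers of remitters.** At the planning CR rates (section 4), 246 × 0.25 = 61.5 and 123 × 0.10 = 12.3, about 62 v 12. If every one has an event, SE(log HR) = √(1/62 + 1/12) = 0.315, so the 95% limits lie a factor exp(1.96 × 0.315) ≈ 1.86 either side of the estimate.

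**5. Simulation with no true difference.** Assumptions not in the SAP: median time to relapse 5 or 10 months, median relapse to death 4 months, follow-up 6 to 30 months, MEC/FLAG-IDA marrow at 1 month only. Each run uses 62 v 12 remitters, 300 replicates and no stratification. The hazard ratio is ASP2215/control. Each cell gives median 5 / median 10.

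| MEC/FLAG-IDA share of control remitters | Off-schedule relapses recorded | Control remitters with a duration-of-CR event | Duration-of-CR HR | LFS HR |
|---|---|---|---|---|
| 0% | – | 0.63 / 0.47 | 1.05 / 1.00 | 1.00 / 0.99 |
| 60% | none | 0.32 / 0.22 | 1.01 / 1.01 | 1.06 / 0.81 |
| 60% | half | 0.53 / 0.40 | 0.75 / 0.68 | 0.91 / 0.74 |
| 100% | none | 0.12 / 0.06 | 1.00 / 0.98 | 1.04 / 0.68 |
| 100% | half | 0.47 / 0.35 | 0.46 / 0.32 | 0.88 / 0.56 |

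The 0% row should be 1 and shows simulation noise of about 0.05.

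A larger run (3000 per arm, all control remitters on MEC/FLAG-IDA, nothing recorded off schedule) gave these LFS hazard ratios for median relapse and median relapse-to-death in months: 1.19 for (4, 4), 0.94 for (6, 4), 1.02 for (6, 6) and 0.72 for (9, 4).

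**The case against.** Several stronger readings are tempting, and the SAP does not support them.

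- *Control relapses in general go unassessed.* No. LoDAC and azacitidine subjects keep cycle-based marrows.
- *MEC/FLAG-IDA remitters have no scheduled assessment.* Too strong. Footnote k gives any CRc subject a marrow one month after remission and on suspicion of relapse, and requires one at end of treatment. Whether the three-cycle marrow runs on is unclear. Conduct of these regimens is referred to a protocol section not at hand.
- *A relapse reported by telephone is ignored.* The SAP does not say so. It censors deaths without a report of relapse, imputes partial relapse dates (7.11.1) and accepts local marrow and blood results when central ones are missing (6.1.3.3). A telephone-only report is simply given no clear place.
- *Early censoring by itself biases duration of remission.* No. With nothing recorded off schedule, its hazard ratio stays near 1. This defence does not carry over to LFS, where deaths keep some subjects at risk and survivors are dropped.

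Other points stand in part. Telephone follow-up applies to both arms, and ASP2215 subjects who do not resume after HSCT also leave the marrow schedule; the asymmetry comes from time on treatment. Duration of CR/CRh has a sensitivity analysis counting deaths as events, but that adopts the LFS event rule and its censoring problem. Making investigator-reported relapse the tested definition in an open-label trial would bring its own bias, so it should not replace derived relapse.

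**Conclusion.** The point holds for MEC/FLAG-IDA remitters. The log-rank p-values and hazard ratios for LFS, DCRc, DCR and DR, and for duration of CR/CRh through 7.4.6, cannot separate durability of remission from assessment schedule.

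Under the stated assumptions and no true difference, the LFS hazard ratio ranged from about 0.7 to 1.2 with no off-schedule relapse recorded and about 0.6 to 0.9 with half recorded. The duration-of-CR hazard ratio stayed near 1 in the first case, with about half the control events lost at a 60% share and most at 100%. It fell to about 0.3 to 0.75 in the second. The MEC/FLAG-IDA share, relapse timing and off-schedule detection are not in the SAP.

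A reader might infer that the comparison is known to favour ASP2215. That follows only under selective recording; without it, LFS can move either way. These endpoints lie outside the OS, EFS and CR testing hierarchy, and version 4.0 plans no further efficacy analysis (sections 1, 6.1, 7.4). The point therefore bears on how the reported results are read, not on the main conclusions of the trial.

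**What to change.** Keep derived relapse as the main definition. Then:

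1. Add a sensitivity analysis in both arms for LFS, DCRc, DCR, DR and duration of CR/CRh, parallel to the EFS analysis that uses long-term follow-up. Relapse is the earliest of derived relapse, relapse reported in long-term follow-up, and start of subsequent AML therapy with a prior relapse recorded (7.2.9 tabulates this item). Censor at the last contact with known remission status.
2. Present LFS and duration results separately for the high- and low-intensity strata.
3. State that between-arm p-values and hazard ratios for these endpoints are descriptive because assessment was unequal.
4. State whether the three-cycle marrow rule continued after MEC/FLAG-IDA ended, and how a relapse reported only by telephone is classified.

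This applies now as a supplementary re-analysis or, at the least, a caveat on the reported results. It needs programming on follow-up data the plan says are collected, with no extra visit or marrow. First check that the follow-up forms hold usable relapse dates. The downside is that some dates will be investigator-reported and accurate only to the three-monthly call.
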